#### 7.3 Analysis Population

#### 7.3.1 Randomized Population

The randomized population includes all patients who are randomized for treatments. Patients who have a missing randomization number will be included in this population. This includes patients who answer the question "Is the subject to be randomized?" = 'Yes" and with a non-missing "Subject Identification Code".

#### 7.3.2 Intent-to-Treat (ITT) Analysis Population

The ITT Efficacy Analysis population includes all patients from the randomized population who have received at least one dose of study drug and who have an evaluated post baseline efficacy assessment. The efficacy assessments include the evaluation of:

- Non- missing Pure-tone audiometry at Visit 3 or Visit 4
- Non- missing Words-in-Noise Test at Visit 3 or Visit 4
- Non-missing Tinnitus Functional Index (TFI) at Visit 2 or Visit 3 or Visit 4
- Non-missing Tinnitus Loudness (TL) at Visit 2 or Visit 3 or Visit 4
- Non-missing Vertigo Symptom Scale (VSS) at Visit 2 or Visit 3 or Visit 4

#### 7.3.3 Safety Analysis Population

All study participants receiving at least one study treatment dose will be included in the safety analysis, whether or not they complete the study. The safety population is derived from the patients with evidence of receiving the study treatment in the "Drug Accountability" and eCRF form met with the following criteria:

- "Study Medication dispensed?" as 'Yes' and
- "Date of Dispensing" and
- The value entered for "Number of Capsules Taken" is greater than or equals 1 (missing values are excluded)

The safety population will be the primary population for the safety analysis. Analyses on the safety population will be based on actual treatment received.

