#### 7.8 Definitions and Derived Variables

For the statistical analysis, two different doses and placebo will be denoted according to the following table.

| Treatment             | Label           |
|-----------------------|-----------------|
| SPI-1005 po BID 200mg | SPI-1005 200 mg |
| SPI-1005 po BID 400mg | SPI-1005 400 mg |
| Placebo po BID        | Placebo         |

In the following table, the definitions and calculation of derived variables are summarised.

| Variable / Term | Definition / Way of calculation   |  |
|-----------------|---|--|
| Baseline        | The last assessment on or before to the treatment start date. The most recent measurement prior to treatment start regardless of whether the measurement is collected at a scheduled or unscheduled visit will be considered for the baseline.  |  |
| End of study    | The date on which the last patient completes the last visit (includes follow-
up visit).   |  |
| BMI             | Weight in kg / Height in m    |  |
| Treatment Start | 
 
The earliest date of 'date of drug dispense' (Date of dispensing) from Study
 
Drug Dispensing and Drug Accountability eCRF form, where the patient has:
 
Answered 'Yes' to question, Study medication dispensed? And,
 
Recorded at least one capsule used for the question, 'Number of capsules taken'
 
If the drug administration date is unavailable and only the last dose date of the patient is available, then the Randomization date will be considered as the treatment start date.
 
 |  |

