#### 8.1.5 Prior and Concomitant Medication

Prior and concomitant medications will be assessed at screening and at each subsequent study visit. Medications will be coded using WHO Drug Dictionary version MAR2017.

Medication will be classified as prior, if the end date is known and is before the first use of the study medication. Medications that are ongoing or ended after the first use of the study medication will be classified as concomitant. If the end date of the medication is unknown, it will also be considered concomitant. If the end date is partially known, the medication will be considered concomitant, unless the known part of the end date rules out the possibility that the medication could have ended before the start of the study drug.

Prior and concomitant medications will be separately summarized by ATC class (the highest available level) and preferred name for the safety population. The prior and concomitant medications will be listed in a by-patient listing.

This document is confidential and proprietary to Sponsor and EA and for restricted circulation and access only. No part of it may be transmitted, reproduced, published or used by any person/s without prior written authorization.

Version No.: Final 1.0

ECRON ACUNOVA

Sponsor Study No: SPI-1005-251

Sponsor Name: Sound Pharmaceuticals, Inc.

NLS Study Code: SPI -1005 -251

Short Title of Study: SPI-1005-251 (Sound Pharmaceuticals, Inc)

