#### 8.2 Extent of Exposure and Compliance

#### 8.2.1 Treatment Exposure

Treatments will be dispensed at baseline to patients based on the randomized group assignments and the patients will receive the treatment for a duration of 28 days.

The earliest date of 'date of drug dispense' (Date of dispensing) from Study Drug Dispensing and Drug Accountability eCRF form, where the patient has:

• Answered 'Yes' to question, 'Study medication dispensed?' and,

Page 19 of 38

• Recorded at least one capsule used for the question, 'Number of capsules taken'

If the drug administration date is unavailable and the last dose date of the patient is only available, then the Randomization date will be considered as treatment start date.

The treatment end date is taken from the field:

- 'Date of last study medication taken' from 'Study Completion or Early Termination' page. If the date of last study drug administration is missing and there is evidence that the patient has taken study medication, last visit date will be considered as 'Treatment end date'.
- Duration of treatment exposure is derived as treatment end date treatment start date + 1

The duration of treatment exposure will be summarized descriptively by treatment group for safety population. Data listing will be presented for study drug administration.

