#### 8.4 Safety Analysis

#### 8.4.1 Adverse Events

Adverse Events will be coded using the Medical Dictionary of Regulatory Activities (MedDRA version 19.1), the coded terms will be used for summarizing the AE(s).

Page 23 of 38

An AE will be considered as treatment-emergent if the time of onset is on or after the time of the first randomized study drug administration. AEs with unknown start dates will be counted as treatment-emergent unless the AE resolution date is prior to the study drug start date. If the start date is partially missing, AE will be considered treatment-emergent unless the known part of the start date or the end date rules out that it occurred after the start of the study drug.

An overall summary table which summarizes, the number and percentages of patients with adverse events, treatment emergent adverse events, serious adverse events, adverse events leading to death and adverse events related to study drug will be provided by treatment groups.

Patients experiencing any adverse events will be summarized by Preferred Term (PT), SOC and treatment. Furthermore, listings of SAEs and AEs that lead to withdrawal will be provided. The number and percentage of patients with at least one TEAE, SAE and discontinuation of study treatment due to AE (DAE) will be summarized by system organ class, preferred term and treatment group.

Adverse Events will be summarized by System Organ Class, Preferred Term and Treatment for Any Adverse Events, Serious Adverse Events, Adverse Events leading to medication discontinuation, Adverse leading to death, Adverse Events by severity, Adverse Events by outcome and Adverse Events by relationship.

A patient experiencing the same AE multiple times will be counted only once for that preferred term. Similarly, if a patient experiences multiple AEs within the same system organ class that patient will be counted only once in that system organ class. In summaries by severity or by relationship, if a patient has the same AE on multiple occasions, the highest severity, and the closest relationship to study drug, respectively, will be used for summary.

All information pertaining to adverse events noted during the study regardless of treatment emergent or not will be listed by patient, detailing verbatim, preferred term, system organ class, start date, stop date, TEAE status, severity, outcome, action taken and causal relationship to the study drug.

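### The safety-set derivation drops dosed patients who have no capsule count, the missing last-dose-date rule has no cap, and the partial medication end-date rule is reversed

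*SAP*

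**What the plan says.** **Safety set.** SAP 7.3.3 opens with an unconditional definition: "All study participants receiving at least one study treatment dose will be included in the safety analysis, whether or not they complete the study". It then builds the set from the drug accountability form. The drug must be marked as dispensed, a dispensing date must be present, and the number of capsules taken must be a value that "is greater than or equals 1 (missing values are excluded".

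The ITT set in SAP 7.3.2 takes randomized patients "who have received at least one dose of study drug and who have an evaluated post baseline efficacy assessment" and sets no capsule-count condition. Treatment start in SAP 7.8, repeated in 8.2.1, is the earliest dispensing date for a patient with "Recorded at least one capsule used for the question". If only the last-dose date is available, it falls back to the randomization date.

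**Treatment end.** SAP 8.2.1, in line with 7.8, reads "If the date of last study drug administration is missing and there is evidence that the patient has taken study medication, last visit date" and takes that visit date as the end of treatment. Exposure is end minus start plus 1.

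**Prior and concomitant medication.** The base rule in SAP 8.1.5 is: "Medications that are ongoing or ended after the first use of the study medication will be classified as concomitant". A medication with a partly known end date counts as concomitant, with this exception: "unless the known part of the end date rules out the possibility that the medication could have ended before the start of the study drug". The matching adverse-event rule in SAP 8.4.1 treats an event with a partial start date as treatment-emergent, with this exception: "unless the known part of the start date or the end date rules out that it occurred after the start of the study drug".

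**The concern.** Each of these rules gives a wrong result if it is programmed as written.

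1. The safety criteria contradict the definition above them. A patient who took drug but has no recorded count, for example because the drug was never returned, meets the definition and fails the derivation. Since ITT carries no count condition, such a patient could be in ITT and not in Safety.
2. The last scheduled visit falls four weeks after dosing ends. Using it as the last-dose date credits off-treatment time as exposure.
3. The medication clause removes concomitant status exactly when the date shows that the medication continued past the start of study drug. It keeps that status when the date shows that the medication had already stopped.

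Safety is the first primary objective in Protocol 1.1 and SAP 5.1. The safety set is the denominator for adverse-event rates and the set used for the exposure and medication summaries.

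**Working it through.** **1. Safety flag.** Applying the three criteria in SAP 7.3.3 literally to a dispensed patient with a dispensing date:

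| Capsule count | Dosed? | By the definition | By the criteria |
|---|---|---|---|
| 28 | yes | in | in |
| missing | yes | in | out |
| 0 | no | out | out |

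Drug is dispensed at two visits. On a natural reading one valid count of at least 1 keeps a patient in, so the loss falls on patients with no count from either dispensing.

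The documents give no rate of missing counts, so the effect can only be shown under assumed numbers. Take 40 patients per arm (SAP 7.6) and an assumed 4 with an event: 4/40 = 10.0%, exact 95% CI 2.8% to 23.7%. If k patients are dropped:

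| k | All had the event, (4−k)/(40−k) | None had it, 4/(40−k) |
|---|---|---|
| 1 | 3/39 = 7.7% | 4/39 = 10.3% |
| 2 | 2/38 = 5.3% | 4/38 = 10.5% |
| 3 | 1/37 = 2.7% | 4/37 = 10.8% |
| 4 | 0/36 = 0% | 4/36 = 11.1% |

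**2. Exposure.** Inputs are 28 days of treatment (SAP 8.2.1), Visit 4 at Day 56 ± 3 (Protocol 1.3), and an assumed start on Day 1.

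- Planned figure: 28 − 1 + 1 = 28 days, as the SAP states.
- Last-dose date missing, Visit 4 attended: 53 to 59 days. 53/28 = 1.89 and 59/28 = 2.11 times the plan.
- The same for a patient who in fact stopped at Day 14: 53/14 = 3.8 to 59/14 = 4.2 times the truth.
- Shift in the mean of a 40-patient arm for each affected patient who took 28 days: (53 − 28)/40 = 0.63 to (59 − 28)/40 = 0.78 days.
- With an assumed four such patients, the mean moves from 28 to 28 + 4 × 0.625 = 30.5, up to 28 + 4 × 0.775 = 31.1 days.

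Protocol 1.1 provides two two-week supplies, so 53 to 59 days also exceeds what the dispensed drug covers on schedule.

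**3. Partial medication end date.** Assume first dose on 10 May and an end date known only to the month:

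| End date | Can an end before 10 May be ruled out? | Clause as written | Base rule / true status | Clause reversed |
|---|---|---|---|---|
| March | no | concomitant | ended before start | prior |
| May | no | concomitant | undetermined | concomitant |
| June | yes | not concomitant | concomitant | concomitant |

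The two dates that settle the question come out wrong. Only the ambiguous one comes out as intended. The adverse-event rule in SAP 8.4.1 has the opposite, correct direction.

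**The case against.** The strongest reply is about weight. Only the first rule touches adverse-event rates. The end-date rule feeds a descriptive exposure summary: treatment-emergent status has no end limit, and compliance uses capsule counts. The medication rule feeds two descriptive tables, and its intent is clear from the sentence before it. This stands, and the second and third rules alone would be minor corrections.

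The first rule is also narrow. It needs a patient with no usable count from either dispensing. The ITT-but-not-Safety case further needs a later efficacy assessment, and the SAP does not say how dosing is derived for ITT. Dropping four patients who all had events is an extreme illustration. This stands too. It limits the likely size, but the criteria still contradict the definition.

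The sponsor signs the population assignment before lock (SAP 11). Tables 14.1.3 and 14.1.4 and the by-patient listings show who was excluded and the underlying records. These make the patients visible and allow review, but they do not correct the rates, the exposure summary or the medication tables.

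Finally, the SAP already has a randomization-date fallback for treatment start. It helps when only a last-dose date exists. However, exposure is summarized for the safety population, and the safety criteria exclude those same patients when they have no count, so the fallback has little effect there.

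**Conclusion.** The point holds for all three rules: they are stated derivations that give wrong results, not missing detail. A dosed patient without any capsule count is removed from the safety set against its own definition. A Visit 4 attendee with a missing last-dose date is credited with 53 to 59 days instead of at most about 28. Every decisive partial medication end date is misclassified.

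How many patients are affected cannot be known from the documents, and neither can the direction of any shift in adverse-event rates. The event counts, the number of affected patients and the calendar dates above are assumptions for illustration. The corrections should be made before database lock. The case for doing so rests mainly on the safety set, and the other two rules can be corrected in the same edit.

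**What to change.** - **SAP 7.3.3:** state that a missing capsule count does not exclude a dispensed patient when there is other recorded evidence of dosing, such as a last-dose date. Exclude when the record shows zero capsules taken. List the accepted forms of evidence so that the rule is not open-ended.
- **Treatment start, SAP 7.8 and 8.2.1:** for these patients use the dispensing date, or else the randomization date. Baseline, treatment-emergent status and exposure can then all be derived.
- **Treatment end, SAP 7.8 and 8.2.1:** when the last-dose date is missing, use the earlier of the last visit and the end of the last dispensed supply.
- **SAP 8.1.5:** class a partly dated medication as concomitant unless the known part of the end date shows that it ended before the start of study drug. In that case class it as prior.

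The cost is wording in four sections and the matching code, with no new data. A few patients whose dosing is uncertain may enter the safety set. The changes do not repair everything. A patient with neither a count nor any other evidence of dosing stays excluded. A patient who received the second supply but stopped at Day 14, with no last-dose date, would still be assigned about 28 days, though no longer 53 to 59.

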#### 7.3.4 Per-Protocol Population

The Per-Protocol Population includes all patients who receive study treatment and have efficacy parameters at Visit 3 and have no major protocol deviations.

#### **Confidentiality Statement**

Version No.: Final 1.0

A ECRON ACUNOVA

Sponsor Study No: SPI-1005-251

Sponsor Name: Sound Pharmaceuticals, Inc.

NLS Study Code: SPI-1005-251

Short Title of Study: SPI-1005-251 (Sound Pharmaceuticals, Inc)

The major protocol deviations include:

- Treatment compliance of <80% and >120%
- Did not meet inclusion/exclusion criteria
- Baseline overall WINT score ≥ 2x Standard Deviations above the mean (rounded down to nearest integer)
- Major protocol deviations impacting the primary efficacy outcome measure.

Page 15 of 38

#### 7.3.5 PK Analysis Population

The PK analysis population includes all randomized patients performing PK evaluations, with the study medication compliance, and have a PK profile at all visits. The patients with major protocol deviations impacting PK results will be excluded from the analysis.

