| SPI-1005
Treatment  | Х                           | Х          | Х          |           |
| Adverse Events                       | Х                           | Х          | Х          | Х         |
| PK                                   | Х                           | Х          | Х          | Х         |

 Urine pregnancy test on CV1 screening visit only.
  SPI-1005 treatment begins after safety labs (CBC, serum chemistry) are reviewed and all inclusion/exclusion criteria are met.

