#### 5.2 Secondary Objectives

To determine the pharmacokinetics at each dosing level of SPI-1005.

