## **6** STUDY DESIGN

#### 6.1 Overview

This clinical trial is a phase 2b, randomized, double-blind, placebo-controlled study to evaluate the safety and efficacy of SPI-1005 in Meniere's disease. The study is planned to be conducted in adult volunteers with Meniere's Disease (probable or definitive diagnosis) with active symptoms in the months preceding study enrollment. Study participants will be randomized into three dosing arms: SPI-1005 200 mg/BID, SPI-1005 400 mg/BID, or placebo (1:1:1). This double-blind study will evaluate both safety and efficacy of the investigational treatment.

Participants aged 18-75 years, with probable or definitive Meniere's disease will undergo baseline testing to assess severity of sensorineural hearing loss, tinnitus and vertigo. This is a multicenter study that includes patients from approximately 12 US sites.

During the study, and 28 days after completion of treatment, participants will be evaluated for safety (adverse events, physical examinations, vital signs and clinical laboratory testing (CBC, serum chemistry). Trough plasma levels of ebselen and its major metabolite (2-glucuronyl selenobenzanilide) will be evaluated using liquid chromatography-mass spectrometry (LCMS) at specified visits. Additionally, plasma will be analyzed for selenium at the corresponding visits. Female participants will receive pregnancy testing at visit 1, and those found to be pregnant will be excluded from the study and monitored for adverse events.

The effect of SPI-1005 on hearing and balance will be evaluated. Hearing will be evaluated at baseline, at the end of 28 days of study treatment, and 28 days after completing study treatment. Tinnitus and vertigo will be evaluated with the Tinnitus Functional Index (TFI) and the Vertigo Symptoms Scale (VSS), respectively. These tests will be administered at baseline, on days 14 and 28

This document is confidential and proprietary to Sponsor and EA and for restricted circulation and access only. No part of it may be transmitted, reproduced, published or used by any person/s without prior written authorization.

Version No.: Final 1.0

Page 10 of 38

Sponsor Study No: SPI-1005-251

Sponsor Name: Sound Pharmaceuticals, Inc.

NLS Study Code: SPI-1005-251

Short Title of Study: SPI-1005-251 (Sound Pharmaceuticals, Inc)

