#### 8.5 Pharmacokinetic Analysis

The PK analysis will be performed based on PK analysis population.

Three (3) mL of blood will be collected at visit 1, visit 2, visit 3 and visit 4. Study participants should be instructed to refrain from taking their morning dose until after their blood is drawn at Clinic Visit 2 and Clinic Visit 3. Sample collection times (actual clock time using 24:00) are to be recorded and will be captured in the CRF.

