#### **Confidentiality Statement**

Statistical Analysis Plan Version No.: Final 1.0 **ECRONACUNOVA** 

Sponsor Study No: SPI-1005-251

Sponsor Name: Sound Pharmaceuticals, Inc.

| NLS Study Code: SPI -1005 -251 | Short Title of Study: SPI-1005-251 (Sound Pharmaceuticals, Inc) |
|--------------------------------|---|

Page 26 of 38

The patient listings as well as Patient's PK profile plots in actual and semi-logarithmic views will be prepared for the PK concentrations. Descriptive summary statistics table including geometric mean & CV% geometric mean will be presented by timepoints and treatment groups. In addition, mean  $\pm$  SD graphs will be prepared for the concentration by timepoints and treatment groups. Descriptive statistics including geometric mean & CV% geometric mean will be presented for the PK

parameters, AUC  $_{0-t}$  (mg. h/L) and  $C_{max}$  (mg/L).

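### The PK population requires a result at every visit, including two off-drug visits, so patients with valid on-drug troughs drop out of all planned PK tables and figures

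*SAP*

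**What the plan says.** The secondary objective in SAP 5.2 is "To determine the pharmacokinetics at each dosing level of SPI-1005". SAP 7.3.5 admits randomized patients who had PK evaluations "with the study medication compliance, and have a PK profile at all visits". It adds a further exclusion: "The patients with major protocol deviations impacting PK results will be excluded from the analysis".

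Sampling is set out in SAP 8.5: "Three (3) mL of blood will be collected at visit 1, visit 2, visit 3 and visit 4". Patients are told to "refrain from taking their morning dose until after their blood is drawn at Clinic Visit 2 and Clinic Visit 3". The same section bases the PK analysis on the PK population and plans concentration summaries as follows: "Descriptive summary statistics table including geometric mean & CV% geometric mean will be presented by timepoints and treatment groups". It also plans summaries of AUC0-t and Cmax.

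The list of reported tables and figures assigns the PK population to Tables 14.2.6 and 14.2.7 and to Figures 15.7 and 15.8. SAP 7.5.1 rules out imputation.

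**The concern.** The protocol synopsis names trough levels as the PK measure. An entry rule for a trough summary should turn on whether the patient has a trough. This one also turns on two samples that cannot be troughs. A patient who gave valid samples at Visits 2 and 3 and then missed Day 56 is left out entirely, and so is one who gave a valid Day 14 sample and then left the study.

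The stake is precision, and possibly representativeness, in answering the secondary objective. By-timepoint means would rest on fewer patients than have usable data at that timepoint, and those who remain are compliant patients with every sample. With a single PK population and no sensitivity set in the plan, no planned summary would show whether the excluded troughs differ from the included ones.

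**Working it through.** **Step 1: which visits are on drug.**

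- Visit 1 is screening/baseline, Day -28 to 1 (Protocol 1.3). A footnote to that schedule says "SPI-1005 treatment begins after safety labs (CBC, serum chemistry) are reviewed and all inclusion/exclusion criteria are met". The Visit 1 sample is therefore before dosing. This is inferred from the schedule; the sample is not labelled pre-dose.
- Visits 2 and 3 are Days 14 and 28, with the morning dose held until after the draw (SAP 8.5). These are the troughs.
- Visit 4 is Day 56. SAP 6.1 times the two post-baseline hearing assessments, which are Visits 3 and 4, "at the end of 28 days of study treatment, and 28 days after completing study treatment".

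So two of the four required results are off drug. Visit 4 alone is enough to make the point.

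**Step 2: what a profile at a visit can be.** The SAP does not define the term. With one 3 mL draw per visit, it can only be that visit's single concentration.

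**Step 3: whether the planned summary needs complete cases.** Concentrations are tabulated by timepoint and group. Each cell needs only the samples taken at that timepoint.

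**Step 4: size.** There is no figure in the plan to reproduce: neither document as supplied gives a PK sample size or a missing-sample rate. The inputs are 40 patients per arm (SAP 7.6) and an assumed dropout rate d per interval, with q = 1 − d. Visit 1 is taken as complete because eligibility and randomization happen there. Dropout is taken as monotone. Exclusions for non-compliance or PK-impacting deviations are not counted.

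Expected patients per arm are 40q with a Visit 2 sample, 40q² with both troughs and 40q³ with all four visits. With the same SD, the standard error of a mean varies as 1/√n. The ratio of the SE under the all-visits rule to the SE on available samples is √(q²/q³) = q^−0.5 at Visit 3 and √(q/q³) = q^−1 at Visit 2.

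| | d = 5% | d = 10% | d = 15% |
|---|---|---|---|
| Visit 2 sample, 40q | 38.0 | 36.0 | 34.0 |
| Both troughs, 40q² | 36.1 | 32.4 | 28.9 |
| All four visits, 40q³ | 34.3 | 29.2 | 24.6 |
| SE ratio at Visit 3 | 1.03 | 1.05 | 1.08 |
| SE ratio at Visit 2 | 1.05 | 1.11 | 1.18 |

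Among patients with both troughs, the share removed is 1 − q³/q² = d, that is 5%, 10% or 15%. Patients with a Visit 2 trough who are removed number 38.0 − 34.3 = 3.7, 36.0 − 29.2 = 6.8 or 34.0 − 24.6 = 9.4 per arm.

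**The case against.** The best defence is AUC0-t. It and Cmax are the only secondary parameters named in SAP 6.2.2, and with one draw per visit an AUC taken across visits would plausibly need every timepoint. That stands as far as it goes, although the SAP does not say that this is how AUC is derived. It could justify a completeness rule for the parameter table (14.2.7). It does not justify filtering the concentration table (14.2.6).

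The compliance condition also has a purpose. A trough after missed doses does not describe PK at the assigned dose, so a revised rule should still screen the dosing that bears on each sample.

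The term profile is undefined, and only the protocol summary is available, so a fuller PK section might say more. The natural reading is nonetheless the strict one.

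Three stronger readings are tempting, and the documents do not support them:

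- *The losses are large.* If all four samples, Visit 1 included, went missing independently at 5%, 10% or 15%, 40q⁴ would leave 32.6, 26.2 or 20.9 patients, with standard errors up 8%, 17% or 28% (q^−1.5). A randomized patient is unlikely to lack the Visit 1 sample that often, and missed visits tend to fall in the same patients.
- *The reported troughs are biased, or safety conclusions suffer.* That requires stopping to be related to exposure, which nothing in the documents shows. No exposure–safety analysis is planned, and the safety population keeps everyone who took at least one dose.
- *The data disappear.* Listings 16.2.5.6 and 16.2.5.7 carry no population label, so excluded values may still be listed. Exclusions and their reasons are reported in Tables 14.1.3 and 14.1.4 and Listing 16.2.2.1.

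**Conclusion.** The point holds as a defect in a stated rule. Followed as written, SAP 7.3.5 leaves valid on-drug troughs out of every planned PK table and figure because an off-drug sample is missing, and the by-timepoint concentration summaries gain nothing from it.

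The size is modest at low dropout and appreciable at higher dropout: about 34, 29 or 25 of 40 per arm kept, against 36, 32 or 29 with both troughs. These figures rest wholly on the assumed rates and pattern in the working. Selection towards compliant completers is a possibility that the plan cannot check, not a demonstrated bias. PK is a descriptive secondary objective here, and the planned efficacy tests and safety summaries use other populations.

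**What to change.** Replace the single definition in SAP 7.3.5 with a PK concentration population: all treated patients, in all three groups, with at least one evaluable on-treatment sample (Visit 2 or Visit 3) and no deviation or missed dosing that affects that sample. Placebo should stay in, because PK is summarised by treatment group and plasma selenium is measured at the same visits.

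Summarise each timepoint on the samples available and show n. Show Visit 1 and Visit 4 results where they exist, without requiring them for entry. Apply a complete-sample requirement only to AUC0-t or Cmax, where the derivation needs it, and state that derivation. Keep the compliant complete-case set as a sensitivity table.

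The cost is SAP wording, a population label on Tables 14.2.6 and 14.2.7 and Figures 15.7 and 15.8, and one extra table. No new data are needed. The downside is that n will differ between timepoints and between the concentration and parameter tables, which footnotes can explain.
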